Study Protocol

Protocol Title: Utilization of Confocal Microscopy during Cardiac Surgery

Document Date: October 19, 2018

IRB Approval Date: October 31, 2018

NCT Number: NCT03189134

Utilization of Confocal Microscopy during Cardiac Surgery

A. Specific Aims/Objectives

This is a pilot study, exploring the safety and feasibility of using diluted fluorescein sodium with fiberoptic confocal microscopy during cardiac surgery.

- The primary aim of this study is to evaluate the safety of using diluted fluorescein sodium during cardiac surgery.
- A secondary aim of this study is to evaluate the feasibility of using this imaging modality. Feasibility will be evaluated in two ways: logistically and technologically.
 - Logistical feasibility will be evaluated by measuring increased time on bypass, rate of enrollment, and the ability to incorporate this imaging modality into standard OR procedures.
 - Technological feasibility will center on the ability to capture quality image files. A quality image file is defined as an image file where a rater can visualize the distinguishable features of the tissue type (cardiac tissue, conductive tissue) in order to classify that tissue type correctly.

B. Background and Significance

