Once the imaging procedure has been completed, the heart surface will be washed with saline and evacuated using a suction apparatus, to ensure all fluorescein has been removed and will

not enter the circulatory system. After that, the remainder of the operation will proceed in the usual fashion. As per standard of care for patients undergoing cardiac surgery, an intraoperative echocardiogram will be performed after the subject is separated from bypass.

The expected hospitalization for the Atrial Septal Defect (ASD) is 3-5 days post-operation. It is not expected that participation in this study will increase the post-operative hospital stay or post-hospitalization recovery. The principal investigator (PI) and research team will monitor clinical labs, electrocardiograms (EKGs), and echocardiograms for any evidence of adverse events. No additional follow-up testing, outside of standard clinical monitoring, are planned. In accordance with standard of care, all subjects will receive a pre-discharge EKG and trans-thoracic echocardiogram.

Image files will be exported out from the Cellvizio system, de-identified, and provided to the blinded raters. The image files will be assessed for quality and the ability to discriminate tissue types.

(2) Patient Selection and Inclusion/Exclusion Criteria

Patients undergoing cardiac surgery for ASD repair at Boston Children's Hospital will be enrolled in this study. Surgery for ASD repair exposes the conduction system of the heart, allowing access to the AWM and nodal tissue for image capture by the Cellvizio system. Congenital heart defects such as ASD are most often diagnosed and repaired in infants and children, which is why conducting this study in a pediatric population is appropriate. Additionally, the FCM has a pre-defined field of focus, with a depth ranging from 55 to 65 μm . Therefore, this technology is more suited to pediatric hearts, as adult hearts are thicker and the conductive tissue may be too deep to be identified using this method.

Inclusion criteria:

- Males and females between 30 days and 21 years old
- Undergoing elective surgery for closure of isolated secundum atrial septal defect
- Both parents attend pre-operative clinic appointment, to provide 2 parent consent, or an adult participant (age 18-21) may provide consent for him/herself

Exclusion criteria:

- Prior history of adverse reaction to fluorescein sodium
- Prior history of renal failure or abnormal renal function

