The probe will be used in direct contact with the cardiac tissue with a pressure of approximately 0.7 mmHg, which is less than 1% of diastolic blood pressure. The maximum laser energy that the system is capable of delivering is 15 mW at 480 nm. This power and wavelength has been approved by the FDA for direct in-vivo imaging for various body tissues, including gastrointestinal, urogenital, and pulmonary. The proposed application is approximately 80% less than the maximum allowable retinal exposure, according to the IEC 60825-1 standard.

(4) Definition of Primary and Secondary Outcomes/Endpoints

Primary Outcome: All adverse events will be collected and relatedness to study participation will be determined. Complications will be compared to average complication rates for ASD repairs.

Hypothesis: Subjects will not experience a higher rate of adverse events than is expected in a clinical setting (<3-4% for all types of adverse events).

Secondary Outcome: The logistical feasibility of conducting FCM imaging during cardiac surgery.

Hypothesis: The study procedure will be logistically feasible in terms of added time on bypass and the ability to incorporate FCM imaging into standard cardiac surgery OR procedures. The rate of enrollment will be evaluated separately.

Secondary Outcome: The quality of the FCM image files collected, defined as the ability of observers to distinguish features and discriminate between working myocardium and nodal tissue.

Hypothesis: Blinded raters will be able to use the FCM image files to distinguish features and discriminate between working myocardium and nodal tissue.

(5) Data Collection Methods, Assessments, Interventions and Schedule (what assessments performed, how often)

Standardized demographic and clinical assessments of all study participants will be performed via medical record review prior to and after surgery until the subject is discharged from the hospital. Images will be obtained during surgery and saved using Cellvizio Software and Viewer. The image files will be de-identified and provided to blinded raters for analysis. Medical records of enrolled subjects will be reviewed post-surgery while the subject is inpatient in the hospital. Adverse events will be abstracted from the record and recorded on a CRF and input into an InForm database.

(6) Study Timeline

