FCM image files obtained for the study will be stored on a password-protected hard drive connected to the Cellvizio system. The image files will be exported, labeled only with the subject's study ID number, and provided to the blinded raters for analysis.

G. Quality Control Method

All study related tasks will follow Good Clinical Practice guidelines. A manual of operations (MOO) will be developed to detail the specific procedures to be conducted and data to be collected. Any significant deviations or exceptions to the protocol will be reported to the IRB and FDA in addition to being discussed among the investigators, and the PI will develop and implement a plan of action as needed (e.g. modification to MOO, study amendment, etc.). The PI will ensure the retention of all necessary records and reports for a minimum of 2 years after the discontinuation of the IND. The FDA will be allowed access to these records. A record of accountability of all investigational drug dispositions will be maintained, including batch and lot numbers and storage records.

H. Data Monitoring

Monitoring and auditing procedures as outlined in the Monitoring Plan will be followed to ensure that the entire study is conducted, documented, and reported in accordance with the IRB approved protocol, the International Conference on Harmonization (ICH) Good Clinical Practice (GCP) Guidelines, and applicable regulatory requirements of Boston Children's Hospital.

Monitors will review and verify protocol compliance with particular focus on AE/SAE reporting, CRF data, source documentation, informed consents, and any other study-related documentation, including review of hospital pharmacy procedures, drug accountability documentation, and drug storage facilities and records.

I. Data Analysis Plan

The FCM image files will be provided post-surgery to blinded raters, who will attempt to categorize the image files as either myocardium or nodal tissue. The raters will note if the image quality is not high enough to discriminate tissue types.

J. Statistical Power and Sample Considerations

This is a single site, descriptive, pilot study, so no power calculations have been performed. Six subjects will provide enough images to determine the feasibility of a larger randomized trial, to be performed in the future.

K. Study Organization

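### Image files reach the blinded raters labelled with the subject's study ID, so raters can link files from one heart and the ratings may not be pure single-image judgements

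*Protocol*

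**What the plan says.** Section F (Data Management Methods) fixes the label on the exported files, which bear only the subject's "study ID number, and provided to the blinded raters for analysis". Section D(1) describes the same step as "Image files will be exported out from the Cellvizio system, de-identified, and provided to the blinded raters", and section D(5) repeats that the files are de-identified. The protocol mentions no code for each file, no random order across subjects and no one-at-a-time display.

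The unit of assessment is the single file. Section A states: "A quality image file is defined as an image file where a rater can visualize the distinguishable features of the tissue type", and adds that this is "in order to classify that tissue type correctly". Section D(4) makes image quality a secondary outcome, "defined as the ability of observers to distinguish features and discriminate between working myocardium and nodal tissue". Section I gives the task to raters "who will attempt to categorize the image files as either myocardium or nodal tissue", with a note where quality is too low to decide.

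**The concern.** De-identification protects privacy. It does not hide which files belong together. A rater who sees the same study ID on several files can set them beside each other, notice which look alike, and label them relative to one another. Such a call uses information from outside the file being rated, while the endpoint asks what that file shows.

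At stake is the meaning of the technological-feasibility result. Section J expects the images from six subjects to settle whether a larger randomized trial is feasible. If the ratings mix single-image reading with within-heart comparison, the reported result cannot be read cleanly as either. Once the raters have seen the linked files, those ratings cannot be made independent of the link afterwards.

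**Working it through.** The protocol gives no accuracy target, sample-size calculation or agreement measure for the rating, so there is no planned figure to reproduce. The check has two parts.

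**1. What the protocol fixes and what it leaves open**

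- Fixed: the label is the subject's study ID (section F); the endpoint is per file (sections A and I); there are six subjects (section D(1)).
- Open: the number of files per subject, whether each subject yields both tissues, and whether raters view a subject's files together. Section D(2) says the operation gives access to both working myocardium and nodal tissue. Section D(1) speaks of one region of interest, imaged for about 90 seconds.

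So linkage is possible by rule. Its use, and its effect, are not determined.

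**2. Illustration of direction and size (all model inputs are assumptions)**

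Take an equal-variance normal model with total SD 1 within each tissue. The tissue means are *d* apart and a share *ρ* of the variance is common to all files from one subject. Each subject supplies *m* files of each tissue.

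- Files judged singly: accuracy *A* = Φ(*d*/2), so *d*/2 = z(*A*).
- Files judged against the subject's own mean: the shared part cancels and the remaining variance is (1 − *ρ*)(1 − 1/(2*m*)). Accuracy is Φ( z(*A*) / √[(1 − *ρ*)(1 − 1/(2*m*))] ).

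Worked case: *A* = 0.80, z = 0.8416, *m* = 1, *ρ* = 0. Then 0.8416/√0.5 = 1.190 and Φ(1.190) = 0.883.

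| Single-file accuracy | m=1, ρ=0 | m=1, ρ=0.6 | m=3, ρ=0 | m=3, ρ=0.6 |
|---|---|---|---|---|
| 0.60 | 0.64 | 0.71 | 0.61 | 0.67 |
| 0.70 | 0.77 | 0.88 | 0.72 | 0.82 |
| 0.80 | 0.88 | 0.97 | 0.82 | 0.93 |
| 0.90 | 0.965 | 0.998 | 0.92 | 0.987 |

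With both tissues present, contrast raises accuracy in every case shown, by about 1 point (0.60, *m* = 3, *ρ* = 0) to about 18 points (0.70, *m* = 1, *ρ* = 0.6).

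**One tissue per subject.** A rater who still splits the files around the subject's mean is right half the time by symmetry: 0.50, against a single-file accuracy of, say, 0.70 to 0.95. The sign reverses.

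**Near the preclinical level.** Section C reports sensitivity 99.2% and specificity 98.0% for human examiners. With equal numbers of each tissue the mean is (99.2 + 98.0)/2 = 98.6%, so inflation cannot exceed 100 − 98.6 = 1.4 points.

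**The case against.** The strongest reply is that nothing shows the raters will use the link. The sentence in section F is mainly a confidentiality provision, and display order is the sort of detail that the manual of operations announced in section G, or an analysis plan, may settle. This stands in part: side-by-side viewing is a possibility, not a stated procedure. But the label itself is not left open. Section F fixes it, and a later document that recoded the files would depart from that text.

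A second reply is that reading linked images may be no less realistic than reading shuffled ones. Section B describes real-time imaging at up to 200 images per second, and a surgeon moving a probe over one heart would also be able to compare sites. This too stands: the protocol does not say that intraoperative use would rest on one image alone. The narrower mismatch remains, because the endpoint as written is per file.

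Two further inferences should be resisted. A reader might conclude that agreement between raters is inflated, but the protocol plans no agreement measure. A reader might also expect hidden IDs to make the file-level results independent. Files from one heart remain correlated whether or not the ID shows; recoding removes only the rater's knowledge of the link.

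**Conclusion.** The point holds in a limited form. By a stated rule, raters can see which files share a heart, while quality and classification are defined for each file. The ratings may therefore not be pure single-image judgements.

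A reader might go further and infer that discrimination is overstated, even by a definite amount. For example, assume tissues 2 within-subject SDs apart and a between-subject SD of 1.0 to 1.5 times the within-subject SD. Accuracy is then Φ(1/√2) = 0.760 to Φ(1/√3.25) = 0.710 for files judged singly, against Φ(1) = 0.841 when the rater knows each subject's midpoint: a gap of 8 to 13 points. The arithmetic is right, but the protocol supports neither the assumed SDs nor the sign. Upward bias needs both tissues from a subject, files viewed together, and a rater who chooses to contrast them. None of these is stated.

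Severity is minor. The point affects one secondary outcome of a six-subject descriptive pilot with no accuracy threshold, and it leaves the primary safety aim untouched.

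**What to change.** In section F, replace the study-ID label on the files sent for rating with a random code for each file, unrelated to the subject. State that files are presented in random order across all subjects. State also that the key, holding subject and recorded anatomical site, is kept from the raters until all ratings are locked. Section I can refer to this.

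The cost is a sentence or two of protocol text and a renaming step at export. Patients, the operation and the sample size are unaffected. It must be in place before any file goes to a rater.
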